Within the clinical context in which IVF treatment is carried out, it is important to ascertain whether the modulation in microbiome caused by an intervention remains long enough to impact on the outcome of a subsequent treatment. In this regard, the key question becomes whether or not the impact of the intervention is still detectable one months after the intervention. The primary endpoint will therefore be the proportion of participants who demonstrate lactobacillus rich microbiome at one month follow up after randomization.

The planned size and duration of this study are based on the following considerations.

1. It is assumed that 80% of women randomized to the intervention will demonstrate a lactobacillus dominant vaginal microbiome on retesting later in the cycle, whereas 20% of those randomized to the placebo will do so, reflecting the impact of other modulating factors independent of the intervention.
2. It is assumed that subsequent spontaneous conversions between lactobacillus dominant and non-dominant profiles will occur in both groups at a similar rate, and it is estimated that this will occur in 20% of women.
3. Given these figures, after the intervention/placebo, it is estimated that 64% of those randomized to the intervention will show a lactobacillus dominant microbiome, one months following the intervention compared to 36% of those receiving the control intervention. In order to show this difference in proportions with 80% power with p value less than 0.05, 37 patients in each arm will be required.
4. Previous studies have reported that around 40% of women embarking on IVF treatment have a lactobacillus poor microbiome and that this can be associated with a poor outcome. This percentage with this microbiome profile is therefore likely to be higher in the study population consisting largely of women with a history of repeated IVF failures. We therefore anticipate that with the current referral rate to the Implantation Clinic and from the patients undergoing treatment in our Fertility Clinic diagnosed with a sub-optimal microbiome, 37 women and 37 controls can be recruited within a period of one year.

Differences between the intervention and control group in the primary endpoint will be tested for significance using the χ^2 test. The significance level will be set at a p-value less than 0.05.

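### The one-month rates of 64% and 36% do not follow from the assumptions they are said to rest on; the natural reading gives 68% and 32%, and 37 per arm has 80% two-sided power under neither pair

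*Combined protocol and SAP*

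**What the plan says.** The passage is in the combined protocol and SAP, III. Methods, under the heading on statistical considerations, primary endpoint and size, items 1 to 3.

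- Item 1, early retest: "It is assumed that 80% of women randomized to the intervention will demonstrate a lactobacillus dominant vaginal microbiome on retesting later in the cycle". The corresponding placebo figure is 20%.
- Item 2, later change: "subsequent spontaneous conversions between lactobacillus dominant and non-dominant profiles will occur in both groups at a similar rate". The size put on this is one woman in five (20%).
- Item 3, presented as following from those figures: "it is estimated that 64% of those randomized to the intervention will show a lactobacillus dominant microbiome". For the placebo arm at the same time point the figure is 36%.
- Item 3, sample size: "In order to show this difference in proportions with 80% power with p value less than 0.05, 37 patients in each arm".

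The primary comparison is a chi-square test. Of the threshold the section says "The significance level will be set at a p-value less than 0.05". It does not say whether the test is one- or two-sided, or whether a continuity correction applies.

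**The concern.** Item 3 offers the two one-month rates as a consequence of items 1 and 2. Item 2 speaks of movement between the two profiles, in both groups and at a similar rate. The printed figures let women in the intervention arm only lose dominance and women in the placebo arm only gain it. No such arm-specific rule is stated anywhere.

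These rates are the design effect for the primary endpoint. If the derivation and the printed pair disagree, the plan supports two different effect sizes. A reader then cannot tell whether 37 per arm is comfortable or too small, and that bears on how a non-significant result would be interpreted.

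**Working it through.** **Inputs.** Early dominance 0.80 (intervention) and 0.20 (placebo), from item 1. Conversion 20%, from item 2. Target 80% power, p < 0.05 and 37 per arm, from item 3.

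**Step 1. Reproduce the printed rates.**

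- Intervention: 0.80 x (1 - 0.20) = 0.64. This omits the gain among the initially non-dominant, 0.20 x 0.20 = 0.04.
- Placebo: 0.20 + 0.80 x 0.20 = 0.36. This omits the loss among the initially dominant, 0.20 x 0.20 = 0.04.
- In each arm 0.80 x 0.20 = 16% of women move (0.16 x 37 = 5.9). Item 2 says 20% (0.20 x 37 = 7.4).

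**Step 2. Apply the 20% in both directions.**

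- Intervention: 0.80 x 0.80 + 0.20 x 0.20 = 0.68
- Placebo: 0.20 x 0.80 + 0.80 x 0.20 = 0.32
- Difference: 36 points, against 0.64 - 0.36 = 28 points as printed.

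**Step 3. Could another common rule give 64/36?** Let l be the loss rate and g the gain rate, the same in both arms.

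- If 20% of women convert in each arm, 0.8l + 0.2g = 0.2 and 0.2l + 0.8g = 0.2. Subtracting gives l = g, so l = g = 0.20 and the rates are 68/32.
- To obtain 64/36, -0.8l + 0.2g = -0.16 and -0.2l + 0.8g = 0.16. Adding gives l = g, so l = g = 0.16/0.6 = 26.7%.
- Losses only in both arms: 64/16. Gains only in both arms: 84/36.

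No rule common to both arms gives 64/36 at 20%.

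**Step 4. Where 37 comes from.** With 64/36 and 80% power:

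- One-sided 0.05, unpooled variance: (1.645 + 0.842)² x (0.64 x 0.36 + 0.36 x 0.64) / 0.28² = 36.3, so 37. This matches the plan.
- One-sided 0.05, pooled: 38.4, so 39.
- Two-sided 0.05: unpooled 46.1, so 47; pooled 48.9, so 49; continuity-corrected 55.8, so 56.

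**Step 5. Two-sided 0.05 under each pair.** Power is exact, by summing binomial probabilities over all possible tables with 37 per arm. Sample sizes use the pooled formula.

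| Rates | Power, uncorrected chi-square | Power, Yates | n per arm for 80% | n with continuity correction |
|---|---|---|---|---|
| 68/32 | 88.4% | 83.0% | 30 | 35 |
| 64/36 | 67.7% | 58.7% | 49 | 56 |

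**Step 6. Sensitivity to the common two-way conversion rate** (uncorrected chi-square, 37 per arm).

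| Rate | One-month rates | Power |
|---|---|---|
| 15% | 71/29 | 96% |
| 20% | 68/32 | 88% |
| 25% | 65/35 | 74% |
| 26.7% | 64/36 | 68% |

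**The case against.** The arithmetic is not in dispute, but four points can be made about its weight.

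1. **The reading is not unique.** Item 2 is loose: it gives no separate loss and gain rates and says only that the rate is similar. This stands, and 68/32 is the natural reading, not a proven intention. It does not rescue the printed pair, because 64/36 needs either a different rule in each arm or a rate of 26.7%.
2. **The slip is small and conservative.** It drops 4 points per arm, about 1.5 women of 37, and understates the planned difference. This also stands: under 68/32, 30 per arm would be enough, so the slip by itself does not make the trial too small.
3. **The low power at 64/36 comes from sidedness.** It would exist had 64/36 simply been assumed. That is true, and the two defects should be kept apart: one concerns how 64/36 follows from items 1 and 2, the other how 37 follows from 64/36. They sit in the same item, and mending only one leaves it inconsistent. Correcting sidedness alone would point to 49 per arm, whereas the plan's own assumptions, read naturally, need 30.
4. **Moving to 68/32 removes an apparent shortfall by adopting the larger effect.** This is a fair warning. The sponsor should choose the pair that reflects what it believes about conversion, not the one with the better power figure.

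**Conclusion.** The concern holds. The 64% and 36% are not consequences of items 1 and 2. Two-way conversion at 20% gives 68% and 32%, a difference of 36 points instead of 28. At two-sided 0.05 with 37 per arm, exact power is 88.4% or 67.7% depending on the pair (83.0% or 58.7% with Yates correction), so the stated 80% holds under neither.

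The 68/32 figure assumes that loss and gain rates are common to both arms and that 20% of women convert in each. The power figures assume 37 evaluable women per arm and a two-sided test, which the plan does not state. The 80%, 20% and 20% inputs are the plan's own and were not tested. The error is conservative in direction, but item 3 should be corrected because the primary sample-size justification rests on it.

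**What to change.** Reword item 3 in one of two ways.

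- **A.** Replace 64/36 with 68/32, show the two-way calculation, and state that 37 per arm gives about 88% two-sided power (83% with Yates correction). The text should then no longer call 37 the number required for 80% power, since 30 would suffice (35 with continuity correction).
- **B.** Keep 64/36, label it a direct cautious assumption not derived from items 1 and 2, and replace the stated 80% with about 68% two-sided power (59% with Yates correction).

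In either case, state that the test is two-sided at 0.05 and whether a continuity correction is used. Correct this together with the unstated sidedness behind the 37, so that effect, sidedness and power agree.

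The cost is the wording of item 3, with no change to the sample size or conduct. Under B the plan openly accepts power below 80%; holding 80% at 64/36 would instead need 49 per arm.

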Recent studies have indicated that a vaginal microbiome consisting of < 90% lactobacilli is associated with failure of IVF treatment (Data submitted for publication, ART PRED, Amsterdam) However, it remains unclear whether interventions designed to alter the microbiome are effective in changing the suboptimal microbiome diagnosed with these new tests, or how stable any induced change in microbiome might be. These questions are of particular importance to women planning IVF treatment, as an effective treatment may alter their prognosis in subsequent cycles. A number of approaches have been proposed, such as treatment with antibiotics and the use of probiotics. Vivag Plus (Bifodan, Hundested, marketed by Orkla, Ishøj) is a vaginal probiotic capsule containing lactobacilli species effective in relieving symptoms of bacterial vaginosis (Lægemiddelstyrelsen, 2017). It is hypothesized that this probiotic may also be effective in restoring lactobacilli dominance in the vaginal microbiome in women shown to have a profile associated with implantation failure. To test this hypothesis, the following research questions will be addressed:

Research questions

1. Compared with a placebo vaginal capsule, does the application of a lactobacilli loaded capsule for 10 days change a lactobacillus poor or by predictive vaginal test otherwise unfavorable vaginal microbiome, to a lactobacillus rich or by predictive vaginal test otherwise favorable microbiome in the same menstrual cycle as intervention?
2. Is the change in the microbiome still present one month after the intervention?

From this, our primary hypothesis is that compared with placebo, use of lactobacillus loaded vaginal capsule is associated with a significant increase in the proportion of women who demonstrate a shift from unfavorable to favorable vaginal microbiome.

III. Methods

Study design and population

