74 women diagnosed with suboptimal microbiome from either vaginal swabs or endometrial fluid sampling will be invited to participate in our double-blinded, randomized, controlled pilot study offering lactobacillus treatment to an intervention group of approximately 37 participants. The control group will receive placebo treatment with a placebo vaginal capsule. Information on medical and fertility history will be collected from patient journal after signed written consent from participants. Information on sexual life will be collected when participating in the study. Timing of last intercourse has shown to have an effect on the vaginal microbiome.

The Implantation Clinic

Since April 2017 Zealand University Hospital has been offering additional diagnostic work-up to women experiencing recurrent implantation failure (RIF= more than three consecutive transfers of high quality embryos). Patients demonstrating a suboptimal microbiome, will be invited to participate in the study. The results from the vaginal- and/or endometrial microbiome, are both part of the RIF-study and not part of diagnostic work-up. Information on microbiome from the RIF-study will be given to investigators in the present microbiome intervention study.

Additional subjects will be recruited from women attending the Fertility who have revealed a suboptimal vaginal microbiome following testing by their clinician and who meet the criteria for inclusion in the study.

The following flowchart gives an overview over the complete study.

Study flowchart

Figure 1: Overall study flow chart

[figure not shown]
[figure not shown]

Figure 2

Cycle with intervention (CD=cycle day)

Participant inclusion- and exclusion criteria

Patients diagnosed with suboptimal microbiome

- Age < 43 years
- Non-smoker
- Vaginal and/or endometrial microbiome suboptimal (<90% dominated lactobacilli)
- Attending Implantation Clinic, patient or control, and agreed to be contacted in case of other research study
- Patients attending fertility treatment in the Fertility Clinic in Køge and who have revealed a suboptimal microbiome following testing by their clinician, and who meet the criteria for inclusion in the study.

Exclusion criteria

- Age < 18 years
- Use of oral antibiotics between diagnose and inclusion
- Use of oral or vaginal probiotics with lactobacilli between diagnosis and inclusion

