Participants dropping out before the primary endpoint has been reached, will be replaced by additional recruits. However, it is anticipated that the drop-out will be <5%. Participants dropping out of the study at any point will be followed until the end of the study period for the individual participant. Participants failing to complete intervention with less than 50% of the study trial medicine, will be replaced.

The end of the study is defined as inclusion and test of the last participants one months after the first vaginal examination after intervention. See Figure 2. End of Trial for each participants will be the last visit to the clinic (third visit).

Study duration

Participant recruitment: September 3rd 2018 – December 31st 2019

Data Analysis: January 1st 2020 – February 1st 2020

Publication of results: March 1st 2020 – May 1st 2020

Biological material from participants

Microbiome material from the vagina

Size: One swab imbedded with bacteria from the top of the vagina.

Purpose: deep sequencing 16SRNA and qPCR from the bacteria to verify any suboptimal microbiome.

Analyzing: The vaginal swab will be send to be analysed abroad by ARTPred, in Holland. The samples will be stored and sent in a frozen state (-80 degrees or on dry ice respectively) in small batches of 10-30 samples. Storage of samples will take place in our fertility lab in Køge, where also sample collection will take place. Samples will be kept pseudo- anonymized and will be fully anonymized after the study is complete.

Analysis: ARTPred, The Netherlands will perform analyses. All samples will be sent pseudo-anonymized and in line with data protection legislation and the law of data protection.

Information from patient journals and research biobank

Information on medical and reproductive history will be collected from patient journal. All medical and fertility information from journals will be used within the study and in our Implantation Clinic. No personal information will be sent abroad. Samples sent will be identified with a participant number and date of sample collection. The participants will admit to use of journal medical- and reproductive history via consent forms. The Danish law on data protection will be followed.

A research biobank will be made to store the samples, between collection and analyses. Permission from the Data Protection Agency will be made simultaneously. All samples will be destroyed after analyses.

Data collection

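### The stated 80% power does not fit the planned test: with 37 per arm, the chi-square test at two-sided 0.05 has about 68% power for 64% versus 36%, and sidedness is not declared

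*Combined protocol and SAP*

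**What the plan says.** All references are to the combined protocol and SAP. The section on statistical considerations, primary endpoint, study participants and size sets the primary endpoint as the proportion of women with a lactobacillus-rich microbiome at one month. Item 3 expects 64% on active treatment and 36% on placebo, and states that "to show this difference in proportions with 80% power with p value less than 0.05, 37 patients in each arm will be required".

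The same section names the analysis. Group differences "in the primary endpoint will be tested for significance using the χ^2 test", and "The significance level will be set at a p-value less than 0.05". Neither sentence says whether the test is one- or two-sided, or whether a continuity correction applies.

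Three other statements bear on the point:

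- Under the research questions, the primary hypothesis is directional: the active capsule is "associated with a significant increase in the proportion of women who demonstrate a shift from unfavorable to favorable vaginal microbiome". No one-sided level is attached to it.
- Item 2 of the sample-size section assumes later conversion between favourable and unfavourable profiles at a similar rate in both groups, and "it is estimated that this will occur in 20% of women".
- After the numbered items, the plan says: "Participants dropping out before the primary endpoint has been reached, will be replaced by additional recruits". So 37 per arm is the number meant to be analysed.

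**The concern.** Item 3 ties four quantities together: the two rates, the significance level, the power and the number per arm. They should agree with each other under the test named in the same section, and they do not. A chi-square test on a 2×2 table is non-directional, so p < 0.05 is two-sided unless the plan says otherwise.

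Two things are at stake:

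- **Interpretation.** A non-significant result would be read against a claimed 20% chance of missing the effect. On the plan's own rates that chance is about 32%.
- **An open choice at analysis.** With sidedness undeclared, a favourable result with a two-sided p-value between 0.05 and 0.10 could be called significant or not after the data are seen.

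**Working it through.** **Inputs.** From item 3: p₁ = 0.64, p₂ = 0.36, difference 0.28, n = 37 per arm, target power 80%. From the analysis paragraph: chi-square test, α = 0.05. No allowance for drop-out, because drop-outs are replaced. Normal quantiles: 1.960 (two-sided 0.05), 1.645 (one-sided 0.05), 0.842 (80% power).

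**Step 1. Reproduce the 37.** The sum of the binomial variances is V = 0.64 × 0.36 + 0.36 × 0.64 = 0.4608. The mean rate is 0.50, so the pooled equivalent is 2 × 0.5 × 0.5 = 0.5.

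- Unpooled formula: n = (z_α + z_β)² × V / 0.28²
- Pooled formula: n = (z_α√0.5 + z_β√V)² / 0.28²

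| n per arm for 80% power | Unpooled | Pooled |
|---|---|---|
| One-sided 0.05 | (1.645 + 0.842)² × 0.4608 / 0.0784 = 36.34 | 38.37 |
| Two-sided 0.05 | (1.960 + 0.842)² × 0.4608 / 0.0784 = 46.13 | 48.86 |

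Only the one-sided unpooled value rounds up to 37. The two-sided versions give 47 (unpooled), 49 (pooled), 49 (arcsine) and 56 (continuity-corrected).

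**Step 2. Power of the planned test at 37 per arm, by normal approximation.**

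- Pooled, two-sided: Φ[(0.28 − 1.960 × √(0.5/37)) / √(0.4608/37)] = Φ[(0.28 − 1.960 × 0.1162) / 0.1116] = Φ(0.467) = 68.0%
- Unpooled, two-sided: Φ(0.28/0.1116 − 1.960) = Φ(0.549) = 70.9%
- One-sided: 78.7% pooled, 80.6% unpooled

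**Step 3. Exact power.** Sum the product of the two binomial probabilities over all pairs of counts for which the Pearson statistic exceeds its critical value.

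| Per arm | Rates | Test at 0.05 | Exact power |
|---|---|---|---|
| 37 | 64% vs 36% | Two-sided, uncorrected | 67.7% |
| 37 | 64% vs 36% | Two-sided, continuity-corrected | 58.7% |
| 37 | 64% vs 36% | One-sided, uncorrected | 77.4% |
| 48 | 64% vs 36% | Two-sided, uncorrected | 79.98% |
| 49 | 64% vs 36% | Two-sided, uncorrected | 81.3% |

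**Step 4. Do the rates change the picture?** Item 3's 64% is 0.8 × 0.8, which counts losses only. Its 36% is 0.2 + 0.8 × 0.2, which counts gains only. Applying 20% conversion in both directions in both arms gives 0.8 × 0.8 + 0.2 × 0.2 = 68% and 0.2 × 0.8 + 0.8 × 0.2 = 32%. At 37 per arm the exact two-sided power is then 88.4% uncorrected, or 83.0% with continuity correction.

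**The case against.** The strongest reply is that the authors meant a one-sided test. The hypothesis is worded as an increase, and 37 is what a one-sided unpooled formula gives, so the figure is not a slip of arithmetic. This probably explains where 37 came from, but it does not reconcile the text: directional wording does not declare a one-sided test, and the named test is not one.

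The exact one-sided power of 77.4% should not be pressed as a further failure. Exact power moves in a sawtooth with n: 79.5% at 35 per arm, 81.1% at 36, 77.4% at 37, 77.9% at 38, 79.2% at 39 and 80.7% at 40. The design section speaks of "offering lactobacillus treatment to an intervention group of approximately 37 participants", and a declared one-sided plan of about that size would have roughly 80% power.

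A second reply is that the rates in item 3 are themselves inconsistent with items 1 and 2, and that with 68% versus 32% the trial exceeds 80% power, even with a continuity correction. That is true, and it means the trial is not shown to be underpowered in every case. But item 3 ties 37 per arm to 64% versus 36%, and that statement is wrong as written.

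A third reply is that 68% presumes no continuity correction, on which the plan is silent. This is also correct. A correction would lower the power to 58.7%, so it widens the gap and is one more thing to specify.

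Finally, the design section calls the study a pilot. It nevertheless has a powered comparison with a significance threshold, so the power statement has to be right.

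**Conclusion.** The concern holds. For the test the plan names, at two-sided 0.05 and on the plan's own rates, 37 per arm gives about 68% power (exact 67.7%) rather than 80%. The shortfall is about 12 percentage points of power, or 12 women per arm against the 49 needed. The defect is a one-sided sample size set beside a test that is two-sided by default, with nothing in the text to reconcile them.

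The conclusion assumes an uncorrected Pearson test, 37 analysed per arm, and 64% versus 36%. With 68% versus 32% the chance of missing the effect falls to about 12%. The stated 80% is not the two-sided power under either pair, so item 3 does not tell a reader what the trial can detect. It must be corrected, because it is the only justification given for the size of the primary comparison.

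**What to change.** Keep 74 women. In the analysis paragraph, state that the chi-square test is two-sided at 0.05 without continuity correction. Then restate item 3 in one of two ways:

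- If the rates stay: with 37 women per arm, this test has about 68% power to detect 64% versus 36%.
- If the rates are corrected for two-way conversion: with 37 women per arm, this test has about 88% power to detect 68% versus 32%.

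Rates, sidedness, number per arm and power should be corrected in a single edit, since each depends on the others.

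The cost is one paragraph, with no extra patients and no change to conduct. If the sponsor keeps 64% versus 36% and will not accept 68% power, the alternative is 49 per arm, which is 98 in total and 24 more women. A one-sided test would have to be declared and justified, with the analysis specified to match. Whichever route is taken, the present wording cannot stand.

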The lactobacillus treatment will consist of Vivag Plus vaginal supplements. The vaginal capsules consist of cultures of *Lactobacillus gasseri* and *Lactobacillus rhamnosus* distributed and produced by Bifodan, approved for vaginal use and treatment of suboptimal vaginal bacteria. The vaginal capsule will be administered in the following dose; one tablet every night before sleep after menstruation, repeated for ten days. Each participant will receive a total of 10 vaginal capsules at inclusion. See figure above for details.

Placebo

Participants randomized to receive placebo, will receive supplements similar to the Vivag Plus, without the active substance; *Lactobacillus gasseri* and *Lactobacillus rhamnosus*. Placebo treatment is provided and developed by Bifodan. Placebo will be taken in the exact same dose as the intervention drug, Vivag Plus. Each participant will receive a total of 10 vaginal capsules at inclusion. See figure above for details.

Participants treated with oral antibiotics during the trial period will be excluded from the study. If pregnancy occurs during the study period, the participant will be followed through the rest of the study. The study drug or placebo is safe and harmless to use during pregnancy.

Active study drug

Content

Hard vaginal gelatine capsule, with more than 10^8 CFU of *Lactobacillus gasseri* EB01 DSM14869 and more than 10^8 CFU of *Lactobacillus rhamnosus* PB01 DSM14870.

Manufacturer

The manufacturer will produce, in anonymous packages according to good manufacturing practice (GMP), both active study drug and placebo.

Packaging, labeling, and handling of study drug

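### The primary test has no stated analysis set or missing-swab rule, and the exclusion and replacement rules, taken in their ordinary sense, would leave randomised women out of it

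*Combined protocol and SAP*

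**What the plan says.** Women are randomised after inclusion and written consent (Randomization). Three later events then change who is carried forward:

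- **Oral antibiotics** (Placebo): "Participants treated with oral antibiotics during the trial period will be excluded from the study".
- **Drop-out** (Statistical considerations): "Participants dropping out before the primary endpoint has been reached, will be replaced by additional recruits". Drop-out is expected to stay below 5%.
- **Low compliance** (same section): "Participants failing to complete intervention with less than 50% of the study trial medicine, will be replaced". Compliance comes from returned medicine or, if none is brought back, from the woman's memory (Registration of adverse events and/or reactions).

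The same section gives the primary endpoint as "the proportion of participants who demonstrate lactobacillus rich microbiome at one month follow up after randomization" and names the χ² test at 0.05. It names no intention-to-treat, full-analysis or per-protocol set, gives no rule for a missing one-month swab, and does not say whether the test is continuity-corrected.

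Two statements point towards counting everyone. The planning rate is given for women as randomised: "it is estimated that 64% of those randomized to the intervention will show a lactobacillus dominant microbiome". And for drop-outs: "Participants dropping out of the study at any point will be followed until the end of the study period".

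**The concern.** Replacement restores the head-count of 37 per arm. It does not restore the randomised comparison. If women leave the denominator because of something that happened after allocation, and that event is related to outcome and differs by arm, the two proportions no longer compare like with like.

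There is also a plainer problem. Two analysts could each follow this text faithfully and test different sets of women, and nothing in it would show which was intended. If the choice is left until results are known, it can be influenced by them.

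**Working it through.** **Step 1. What is stated for each group of women.**

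| Group | Followed to one month? | One-month swab? | Counted in the test? |
|---|---|---|---|
| Drop-outs | Yes | Implied | Not stated |
| Oral antibiotic users | Not stated (excluded from the study) | Not stated | Not stated |
| Under 50% of capsules | Not stated (replaced) | Not stated | Not stated |
| Pregnant during the study | Yes (Placebo) | Implied | Not stated |

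The swab is implied for drop-outs because each woman's study period ends at the third visit (Statistical considerations), a swab is taken at the examination held at every visit (Laboratory tests and examinations), and tests fall before treatment, after treatment and one month later (Side effects, risks, and disadvantages).

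**Step 2. Inputs.** From the plan: 37 per arm, 64% v 36% favourable at one month, significance level 0.05, drop-out under 5%. Since 0.05 × 74 = 3.7, that is at most 3 women in total. Assumed: a two-sided test, and every removal pattern below. The plan gives no rate for antibiotic use or low compliance.

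The plan's own 37 per arm for 80% power is matched by a one-sided unpooled calculation (36.34, rounded up). Two-sided exact power at 37 per arm is 67.7%. That is a separate matter, used here only as a baseline.

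**Step 3. Type I error.** Suppose there is no treatment effect and 36% are favourable in both arms. If *k* unfavourable women are lost from one arm and the arm is refilled to 37 at the rate of those remaining, its expected rate is 0.36 / (1 − *k*/37). If 20% of unfavourable women are removed, the rate is 0.36 / (0.36 + 0.64 × 0.80) = 0.413, with 0.64 × 0.20 = 12.8% of the arm removed. Summing the binomial probabilities of all 37 v 37 tables that the χ² test rejects gives:

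| Assumed loss, one arm only | Rate v 36% | Uncorrected | Continuity-corrected |
|---|---|---|---|
| None | 36.0% | 4.8% | 2.8% |
| 1 unfavourable | 37.0% | 4.9% | 2.8% |
| 2 unfavourable | 38.1% | 5.1% | 3.0% |
| 3 unfavourable | 39.2% | 5.6% | 3.4% |
| 20% of unfavourable | 41.3% | 7.1% | 4.4% |

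If the three women are instead replaced by ordinary recruits, each with a 36% chance of being favourable, the uncorrected figure is 5.8%.

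**Step 4. Direction at the plan's 64% v 36%.** The planned difference is 28 points. Losing 3 unfavourable placebo women gives 64 − 39.2 = 24.8 points. Losing 3 unfavourable active women gives 0.64 / (34/37) = 69.6%, and 69.6 − 36 = 33.6 points. With ordinary recruits as replacements the differences are 25.1 and 33.2. The bias can go either way.

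**Step 5. Cost of counting everyone.** Let a share *q* of active women be low compliers who respond like placebo (assumed). The active rate is (1 − *q*) × 0.64 + *q* × 0.36.

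| *q* | Active rate | Difference | Loss of exact power from 67.7% |
|---|---|---|---|
| 5% | 62.6% | 26.6 points | 4.6 points |
| 10% | 61.2% | 25.2 points | 9.5 points |
| 20% | 58.4% | 22.4 points | 19.3 points |

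**The case against.** The strongest reply is that replacement is a recruitment rule and not an analysis rule. Nothing says that replaced women's data are thrown away, the arm size is described as approximate (Study design and population), the planning rate refers to women randomised, and drop-outs are followed to the end. This stands in part. A reader might infer that the plan prescribes an analysis of compliers plus replacements. That is the likeliest reading of the rules, but it is not written, and an all-randomised analysis remains compatible with the text.

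A reader might also infer that drop-outs contribute no one-month swab. The documents do not support that either: as Step 1 shows, the visit and swab schedule implies that it is taken. The gap for drop-outs is only whether it is analysed.

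Third, both clinician and participant are blinded and no side effects are known, so nothing in the documents points to removal that differs by arm. Removal that is equal in both arms and unrelated to outcome causes no bias. This also stands, and it limits the expected harm. It does not tell the analyst whom to count, and the under-5% expectation covers drop-out only.

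Finally, this is a pilot asking whether applying the capsule changes the microbiome, so a prespecified complier analysis could be defended. It would still have to be named. The commitment to CONSORT (Data collection) does not name a set.

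**Conclusion.** The point holds in limited form and should be fixed. The analysis set and the missing-swab rule are absent from the statistical section and from the rest of the text supplied. The stated rules, applied in their ordinary sense, would drop randomised women because of post-randomisation events. For antibiotic-treated women and those under 50% of capsules, neither follow-up nor analysis is stated.

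The documents do not show that the trial's type I error is inflated. Within the anticipated drop-out the effect is small even in an extreme arrangement (4.8% to about 5.6%, or 5.8% with ordinary recruits). The 7.1% figure rests on an assumed 20% removal of unfavourable women from one arm. A continuity-corrected test stays below 5% in every row of the table, but only because it starts at 2.8%; the shift in the compared rates is the same. The size and sign of any real bias are unknown.

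**What to change.** 1. In Statistical considerations, state that the primary analysis includes all randomised women in their assigned arm, and that additional recruits are added to, and do not substitute for, women already randomised.
2. Reconcile the antibiotic-exclusion and replacement sentences with the follow-up sentence, so that the one-month swab is also sought from antibiotic-treated and under-50% women. This concerns data collection and analysis only.
3. Prespecify one missing-swab rule and one alternative as a sensitivity analysis. No single rule is neutral. Counting missing as failure, with 3 of 37 placebo swabs missing at random and none in the active arm, gives 0.36 × 34/37 = 33.1% v 36%: a false 2.9-point benefit and 5.7% type I error (uncorrected).
4. Report the set with at least 50% of capsules and no oral antibiotics as a sensitivity analysis, noting where compliance came from memory.

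The cost is a few sentences and some extra effort to obtain swabs. The real downside is that the estimated effect may be smaller and power lower, by the amounts in Step 5 under the shares assumed there. The edits should be made before unblinding.
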